#### **TEAE Summaries** Table 8.

#### 9.2.3 Adverse Events of Special Interest

Not applicable.

#### 9.3 Laboratory Data

Clinical laboratory values at baseline (screening) and changes from baseline at each assessment time point will be presented by data listings for each treatment group using Safety population.

#### 9.4 Vital Signs

Vital signs (systolic and diastolic blood pressure, pulse rate, respiratory rate, and temperature) at baseline (screening) and changes from baseline at each assessment will be presented by data listings.

#### 9.5 Height and Weight

Height and weight at Screening visit will be summarized as baseline characteristics. Weight will be listed.

#### 9.6 Pregnancy Test

Participants with a positive result for the safety population will be listed.

#### 9.7 Injection Site Response

ISRs are recorded in participant diaries after each treatment (initial and touch-up). Diary Day is derived as diary date - treatment date + 1 (e.g., the day of treatment is diary Day 1). ISR entry includes diary data and eCRF data on Ongoing ISR page. The maximum severity and ISR duration are based on diary data and eCRF data for the specified treatment (e.g., the maximum severity for touch-up treatment is based on diary data and eCRF data after touch-up treatment).

Number (%) of participants will be summarized for each treatment by predefined symptoms. The number of participants with ISR entries (diary data and eCRF data) for

each treatment is used as the denominator for the calculation of percentages. The ISR analyses are listed in Table 9.

Endpoint	Description	Timing	Methodology
ISR severity	Number of participants with ISRs by symptom incidence and categorized by maximum severity reported on Diary and ongoing ISR eCRF	Initial, Touch-up	Frequency counts and percentages
ISR duration	Number of participants with ISRs by symptom incidence and categorized by duration. Duration is defined as number of days from first instance of the symptom to the last instance of the symptom reported on Diary or ongoing ISR eCRF (i.e., date of last ISR - date of first ISR + 1.)	Initial, Touch-up	Frequency counts and percentages, continuous descriptive statistics
Ongoing ISR	ISRs recorded on Ongoing ISR page		Listing

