# 9. Statistical Considerations

A separate SAP will be prepared to provide specifications for all analyses. The plan will be finalized and approved prior to clinical database lock. The database will be locked and analyzed at the end of study (all data collected through the end of the study).

In general, descriptive statistics will be presented. Categorical variables will be summarized with response frequencies and percentages. Continuous variables will be summarized by descriptive statistics for the number of participants, mean, median, standard deviation, Q1, Q3, minimum, and maximum. Where appropriate, 2-sided 95% CIs for mean or proportion will be provided as part of the summary.

Every attempt will be made to collect complete data and limit the occurrence of missing data. No imputation of missing data is planned, except for the primary effectiveness analyses as described in Section 9.4.2.2. Deviations from the analyses planned in the SAP will be documented in the clinical study report.

Statistical analysis activities will be conducted by the Coordinating Investigator or by a third party delegated by the Coordinating Investigator.

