## 9.4. Statistical Analyses

The SAP will be finalized before database lock and will include a more technical and detailed description of the statistical analyses described in this section. This section is a summary of the planned statistical analyses of the most important endpoints, including primary and secondary endpoints.

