#### 9.4.5. Safety Analyses

The safety analysis will be performed using the safety population and will be fully defined in the SAP. The safety parameters will include procedural pain, ISRs, AEs, jaw function assessment, vital signs, concomitant medications and procedures and clinical laboratory values.

Procedural pain will be summarized using response frequencies and descriptive statistics. ISRs reported by participants will be summarized at the participant level by symptom incidence, maximum reported severity, number of ISR days, maximum reported contiguous duration (maximum successive days of the ISR) and total duration days (number of days from first onset day to last occurrence) for initial and touch-up, separately. The summary of procedural pain and ISRs will be done separately for the initial treatment group and the optional treatment group.

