# 1.0 Introduction

This Statistical Analysis Plan (SAP) provides a technical and detailed elaboration of the statistical analyses of the effectiveness and safety data as outlined and specified in the final protocol of Study 1878-701-008 (Amendment 3, 18 January 2022). Specifications of tables, figures and data listings are contained in a separate document.

Unless noted otherwise, all analyses will be performed using SAS Version 9.4 (SAS Institute Inc., Cary, NC 27513) or later under the LINUX operating system.

This SAP includes changes to analyses described in the protocol. Details are outlined in Appendix C.

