#### 9.2.2 Adverse Event Overview

TEAEs will be summarized by treatment group for CP using the safety population. TEAEs will also be summarized by treatment group for TP using the VIT and VOT populations, respectively as described in Table 8. The summaries will be presented using number and percentage of participants with TEAEs as well as the number of events. Additional summaries may be provided when applicable.

An overall summary of TEAEs will be presented as described in Table 8.

A TEAE will be considered a treatment-related TEAE if the TEAE is deemed as related to the study procedure or the study device by the TI. Treatment-related AEs will be summarized by duration, severity, time to onset on/after the most recent treatment, and outcome.

The duration of an AE is defined as the end date of AE minus the start date of AE plus 1.

If more than 1 AE is coded to the same preferred term for a participant, the participant will be counted only once for that preferred term using the most severe and most related occurrence for the severity and relationship to study intervention summaries, respectively.

If the severity of a TEAE is missing, the maximum severity will be assigned to the event for the summary on severity. The value will be displayed as missing in the data listing.

If the relationship to the study intervention is missing for a TEAE, the event will be considered related to the study intervention for the summary. The value will be displayed as missing in the data listing.

Listings of all AEs, TESAEs, TEAEs leading to discontinuation, and death will be presented.

Endpoint	Description	Timing	Methodology
Overall summary	
 
Overall summary only for the following categories:
 
TEAEs
 
Treatment-related TEAEs
 
Treatment-related TEAEs at injection site
 
Treatment-related TEAEs not at injection site
 
TESAEs
 
Treatment-related TESAEs at injection site
 
Treatment-related TESAEs at injection site
 
Treatment-related TESAEs not at injection site
 
Treatment-related TESAEs not at injection site
 
TESAEs at injection site
 
Treatment-related TESAEs not at injection site
 
Treatment-related TESAEs not at injection site
 
TesAEs leading to study discontinuation
 
Deaths
 
	CP, TP	Frequency counts and percentages
TEAEs	

By SOC and PT

By SOC, PT, and maximum severity

	CP, TP	Frequency counts and percentages

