#### Appendix C. Changes to Protocol-planned Analysis

- Add Observed Primary Endpoint (OPE) population as "All mITT population participants who have non-missing Month 6 ATHS assessments for both temples," which will be used for additional sensitivity analysis of primary endpoint, to provide further information on robustness of results.
- Updated number of imputed datasets created from 5 to 30, on handling of missing data for primary effectiveness endpoint, to enhance robustness of multiple imputation results.

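### Does SAP Table 9 need the two injection site response (ISR) duration measures that Protocol 9.4.5 planned and the SAP leaves out?

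*SAP*

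**What the plan says.** Protocol 9.4.5 leaves the full definition of the safety analysis to the SAP, but it also names what it expects. ISRs are to be summarized per participant by incidence, maximum severity, and "number of ISR days, maximum reported contiguous duration (maximum successive days of the ISR) and total duration days". Initial and touch-up treatment are kept apart, as are the initially treated and optionally treated groups. Protocol 9.4 adds that the SAP "will include a more technical and detailed description of the statistical analyses described in this section".

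SAP 9.7 states "The ISR analyses are listed in Table 9". Table 9 has three rows: severity, one duration, and a listing of ongoing ISRs. For the duration row, "Duration is defined as number of days from first instance of the symptom to the last instance of the symptom", using diary and Ongoing ISR eCRF data, with the formula last date minus first date plus 1.

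On departures from the protocol, SAP 1.0 says "This SAP includes changes to analyses described in the protocol. Details are outlined in Appendix C". Appendix C has two entries: the added observed-primary-endpoint population, and "Updated number of imputed datasets created from 5 to 30". The entry for Section 9.7 in the SAP version history records the removal of maintenance-treatment text and an unspecified clarification.

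**The concern.** Two measures named in the protocol are missing from the SAP's own list of ISR analyses, and the SAP does not follow its own rule for declaring such changes. The usual safety net does not catch this. Protocol 9 says "Deviations from the analyses planned in the SAP will be documented in the clinical study report", which covers departures from the SAP and not an item that the SAP has already left out.

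Participant-assessed ISRs are a named safety endpoint in a study meant to support approval. A first-to-last span cannot tell a reaction that persists from one that clears and returns. If many participants had intermittent symptoms, the table would give the length of the window in which symptoms occurred and not how many days participants had them.

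**Working it through.** The plan states no figure to reproduce. The check compares the two texts and then asks what the missing measures could add.

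**Side by side**

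| Protocol 9.4.5 | SAP Table 9 | Declared in Appendix C |
|---|---|---|
| Number of ISR days | absent | no |
| Longest run of successive days | absent | no |
| Total duration, first to last day | present, as last minus first plus 1 | not needed |

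One of three measures is kept. The one kept equals the protocol's total duration. Table 9 reads as complete, with no sign of redaction or a broken table.

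**What the span hides.** The patterns below are illustrations, not data from the documents. Span = last day − first day + 1. ISR days = count of days reported. Run = longest block of consecutive reported days.

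- Days 1-14: span 14 − 1 + 1 = 14; ISR days 14; run 14.
- Days 1, 2, 3 and 14: span 14 − 1 + 1 = 14; ISR days 4; run 3.

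Table 9 shows 14 for both. In general, span ≥ ISR days ≥ run, because every reported day lies within the span and the longest run is made of reported days. With a span of 14 days, the first and last days are fixed as reported, so ISR days can lie anywhere from 2 to 14 and the run from 1 to 14. All three agree when the symptom is uninterrupted. How often it is interrupted is not stated anywhere in the documents, so the size of the loss cannot be estimated and may be zero.

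**What the two measures would bring with them.** They depend on how blank diary days are handled. Take a symptom present on Days 1-14 with the Day 7 entry left blank and counted as absent. The span is still 14, ISR days are 14 − 1 = 13, and the longest run is Days 8-14, which is 14 − 8 + 1 = 7. One blank entry halves the run and leaves the span untouched. The span has its own weakness: a blank first or last symptomatic day shortens it. It therefore bounds the other two measures from above on the same records, but it does not bound true duration.

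Protocol 8.2 has the diary run daily for 30 days. Table 9 also draws on the Ongoing ISR eCRF page, and the documents do not say that this page records presence day by day. A day count or run that extends past Day 30 could therefore need an assumption of continuity. The span needs only the last date.

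**Volume of output.** Protocol 8.2 lists 9 symptoms. With 2 measures, 2 treatments (initial, touch-up) and 2 groups (initially and optionally treated), full restoration is 2 × 9 × 2 × 2 = 72 symptom-level summaries.

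**The case for a change.** The strongest case for a change is that the protocol names three measures and describes two of them in parentheses, so it treats them as different quantities. The SAP undertook to declare its changes and did not declare this one. The daily data are already planned, so restoring the measures, or adding one sentence to Appendix C, costs little.

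The textual part of this stands in full. The SAP should have mentioned the narrowing, and delegating the full definition to the SAP does not excuse the silence.

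A further argument is that the adverse event tables cannot make up for the gap, because "The duration of an AE is defined as the end date of AE minus the start date of AE plus 1" is also a span. That does not hold as put. It assumes that a recurring reaction is entered as a single event, which the documents do not say. If recurrences are entered separately, each has its own dates, and SAP 9.2.2 counts events as well as participants. Those tables cover only ISRs that the treating investigator judges to be adverse events, except at Site 11508, where the version history says all ISRs were reported as such. Whether they show intermittency is open.

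The argument that information is lost is also weaker than it looks. SAP 1.0 puts table specifications in a separate document, which was not available. Absence from the SAP is shown; absence from the study report is not.

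**Conclusion.** The mismatch is confirmed: two of three protocol-named ISR time measures are not in SAP Table 9, and Appendix C does not say so. No change to the plan follows.

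An analyst who follows the SAP as written produces a correct, clearly defined duration that the protocol itself planned. The output is descriptive, carries no hypothesis test, and does not touch the primary endpoint or the gatekeeping sequence. No bias arises and no stated figure is altered. What is forgone is the distinction between continuous and intermittent symptoms, a gain of unknown size that may be nil, against up to 72 further summaries that are sensitive to blank diary days. The remaining defect is one of record-keeping, an undeclared narrowing that a single sentence would cover.

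This rests on three points: Table 9 is complete as it reads; the daily diary is collected as Protocol 8.2 plans, so both measures can still be derived for the diary period if someone asks; and no claim about continuous versus intermittent symptoms will be drawn from the span alone.

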#### Table 9. **Injection Site Response Analyses**

#### 9.8 **Procedural Pain**

Participant assessment of procedural pain (pain during injection) on an 11-point scale ranging from 0 (no pain) to 10 (worst pain imaginable) after initial, touch-up be summarized descriptively.

#### 9.9 Safety Subgroup Analyses

TEAEs and treatment-related TEAEs during CP and TP will be analyzed for all sites excluding site 11508 as well as site 11508 only. Details of the analyses are shown in Table 10.

#### Table 10.TEAE Subgroup Analyses

Endpoint	Description	Timing	Methodology
Overall summary	
 
Overall summary only for the following categories:
 
TEAEs
 
Treatment-related TEAEs
 
Treatment-related TEAEs at injection site
 
Treatment-related TEAEs not at injection site
 
TESAEs
 
Treatment-related TESAEs
 
Treatment-related TESAEs at injection site
 
Treatment-related TESAEs not at injection site
 
Teatment-related TESAEs not at injection site
 
	CP, TP	Frequency counts and percentages
TEAEs	• By SOC and PT	CP, TP	Frequency counts and percentages
Treatment -related TEAEs	• By SOC and PT	CP, TP	Frequency counts and percentages

## 9.10 Other Safety Analyses

Other safety endpoints include global score of jaw functional and concomitant medication and concurrent procedures.

The other safety endpoints will be summarized by treatment groups, for VIT and VOT where applicable.

For Jaw Functional Limitation Scale, the 8-item form (JFLS-8) is used in the study. Raw and change from baseline values of global score (calculated as mean of the available items when no more than 2 items missing) will be summarized using descriptive statistics.

Concomitant medications (Section 7.3) and concurrent procedures (coded using MedDRA) will be listed.

# 10.0 Other Analyses

Not applicable.

# 11.0 Interim Analyses

Not applicable.

## 11.1 Data Monitoring Committee

Not applicable.

# 12.0 Overall Type-I Error Control

All statistical tests will be 2-sided hypothesis tests performed at the 5% level of significance for main effects. A gatekeeping procedure will be used for hypothesis testing of the primary endpoint (ATHS responder) and 2 of the secondary endpoints (responder rates for EI and participant assessments of GAIS) following a predefined sequence to control the overall type I error rate at the 0.05 level. The primary hypothesis must be rejected in order to test the responder rate for EI assessment of GAIS. Additionally, statistical significance must be established for the responder rate for EI assessment of GAIS in order to assess the hypothesis for the responder rate for participant assessment of GAIS.

# 13.0 Version History

	SAP Version History Summary				
SAP Version	Approval Date	Change	Rationale		
1	08 September 2020	Not Applicable	Original version		
2	05 June 2023	Introduction	Section 1.0 added clarification of system information.		
		Administration of Study Treatment	Section 6.0 added clarification footnote to Table 4 on treatment administration summary.		
		Demographics and Baseline Characteristics	Section 7.1 removed ethnicity summary as this study will only include Chinese subjects.		
		Handling of Missing Data for the Primary Effectiveness Endpoint(s)	Section 8.3.2 updated number of imputed datasets from 5 to 30, to improve robustness of multiple imputation results.		
		Secondary Effectiveness Analyses	Section 8.4, added clarification for FACE-Q.		
			Section 8.5, added clarification of analyses methods and description on additional effectiveness analyses.		
		Adverse Events	Section 9.2 removed "maintenance treatment" related description as not applicable.		
			Section 9.2.2, added clarification of treatment-related TEAE.		
			Added clarification to Table 8 TEAE summaries.		
		Injection Site Response	Section 9.7 removed "maintenance treatment" related description as not applicable and added clarification.		

	SAP Version History Summary			
SAP Version	Approval Date	Change	Rationale	
		Safety subgroup analyses	Section 9.9 added safety subgroup analyses of TEAEs, to evaluate the impact of unusual AE reporting rule in Site 11508 (all ISRs were reported as AEs), subgroup analyses of AEs without this site and AEs within this site will be analyzed separately, to provide a holistic picture of AEs profile in this study.	
		Appendix	Removed Appendix Scales and Scoring Algorithms and related descriptions in context to comply with current standard.	

#### Appendix A. Protocol Deviations

Significant protocol deviations will be identified. Unique participants reporting significant protocol deviations will be summarized in total and by treatment group for all randomized or treated participants as described in Table 11. If there are participants who are mistreated, tabulate participants as randomized.

A data listing of significant protocol deviations will be provided. Also, a listing of visits affected by COVID-19 will be included, even if there is no associated significant protocol deviation.

#### Table 11.Protocol Deviation Summary

Endpoint	Description	Timing	Methodology
Significant protocol deviations	Number (%) of participants with significant protocol deviation will be summarized (All randomized)	During study period	Frequency counts and percentages

#### Appendix B. Definition of Adverse Events of Special Interest

Not Applicable.

#### Appendix C. Changes to Protocol-planned Analysis

- Add Observed Primary Endpoint (OPE) population as "All mITT population participants who have non-missing Month 6 ATHS assessments for both temples," which will be used for additional sensitivity analysis of primary endpoint, to provide further information on robustness of results.
- Updated number of imputed datasets created from 5 to 30, on handling of missing data for primary effectiveness endpoint, to enhance robustness of multiple imputation results.

#### Appendix D. List of Abbreviations

Abbreviation	Definition
3D	3-dimensional
AE	adverse event
AO	as observed
ATHS	Allergan Temple Hollowing Scale
CI	confidence interval
СР	control period
EI	Evaluating Investigator
FCS	fully conditional specification
GAIS	Global Aesthetic Improvement Scale
ISR	injection site response
MedDRA	Medical Dictionary for Regulatory Activities
MI	multiple imputation
mITT	modified intent-to-treat
NRI	non-responder imputation
OPE	observed primary endpoint
РСР	post-control period
PI	Principal Investigator
PP	per-protocol
РТ	prefer term
SAE	serious adverse event
SAP	statistical analysis plan
SD	standard deviation
SOC	system organ class
TEAE	treatment-emergent adverse event
TESAE	treatment-emergent serious adverse event
TI	Treating Investigator
ТР	treatment period
VIT	VOLUMA initially treated
VOT	VOLUMA optionally treated
WHO	World Health Organization
